5.5.3. Data Handling Rule

Unless otherwise specified, data handling rules specified in Section 5.2.3.3 will be applied to these secondary analyses. Over time summaries for continuous endpoints will be based on the observed data after treatment failure rules. For binary endpoints, participants with missing response status after applying treatment failures rules will be considered non-responders for the over time analyses.

5.5.4. Analysis Related to HiSCR

- The proportion of participants who achieved HiSCR, the proportion of participants who achieved HiSCR by baseline weight (≤ 95 kg, >95 kg), and the proportion of participants who achieved HiSCR by baseline Hurley stage status will be summarized by treatment group over time.

The proportion of participants who achieved HiSCR will also be summarized over time by treatment groups using observed data after applying treatment failure rules and observed data without considering treatment failure rules respectively as sensitivity analyses.

In addition, the HiSCR will be summarized over time from Week 20 through Week 48 with Week 16 as baseline for the placebo participants who are re-randomized to either guselkumab 100 mg q8w or guselkumab 200 mg q4w group.

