A guselkumab 200 mg SC q4w dose, approximately 4-fold of the approved psoriasis dose (ie, 100 mg SC at Weeks 0 and 4, then 100 mg SC q8w thereafter), is also included in this POC study to determine the HS efficacy resulting from the maximally practicable SC dose of guselkumab.

Participants randomized to placebo will cross over to blinded guselkumab treatment at Week 16, including the 200 mg SC q4w dose and a lower 100 mg SC dose at Weeks 16 and 20, followed by q8w through Week 36, which is the approved psoriasis dose. Based on the results from an open-label ustekinumab HS study, it is likely that the psoriasis dose regimen could provide some clinical benefits. Comparison of the relative efficacy of these two dose groups will provide useful data for determining if a dose higher than the optimal psoriasis dose provides incremental efficacy in HS.

Available preclinical observations and clinical data from other therapies suggest that a dose higher than the psoriasis dose may be needed in HS to achieve optimal efficacy. For example, IL-17+ CD4 T cells were shown to be enriched more than 40-fold in HS-involved skin compared with normal skin, ¹¹ while the ratio was only approximately 2-fold for psoriasis. ⁶ IL-17A gene expression and protein levels have been reported to be highly up-regulated in HS affected skin compared to unaffected skin. ⁷ Additionally, studies have shown similar IL-23/Th17 pathway gene expression in HS- and Crohn's disease-affected tissues, indicating potential commonality in the pathophysiology of these autoinflammatory conditions. ^{16,22} Moreover, an adalimumab Phase 2 dose-ranging HS study found that an adalimumab dosage comparable with that used for Crohn's disease and ulcerative colitis, and essentially twice the psoriasis dose, provided better efficacy compared with the approved psoriasis dose, ⁸ and ultimately became the adalimumab dose approved for HS treatment. Finally, HS patients are generally heavier than patients with psoriasis (median body weight of approximately 94 kg and 89 kg, respectively)^{12,14} and guselkumab exposure has been shown to be lower in heavier participants.

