5.1. Inclusion Criteria

Each potential participant must satisfy all of the following criteria to be enrolled in the study:

- 1. Be a man or a woman at least 18 years of age (or the legal age of consent in the jurisdiction in which the study is taking place).
- 2. Have moderate to severe HS for at least 1 year (365 days) prior to the baseline visit as determined by the investigator through patient interview and/or review of the medical history.
- 3. Have HS lesions present in at least 2 distinct anatomic areas (examples include but are not limited to left and right axilla; or left axilla and left inguinocrural fold).
- 4. Had an inadequate response to an adequate course of appropriate oral antibiotics for treatment of HS (or demonstrated intolerance to, or had a contraindication to, oral antibiotics for treatment of their HS) in the investigator's opinion.
- 5. Have stable HS for at least 1 month (28 days) prior to the screening visit as determined by the investigator through patient interview and/or review of the medical history.
- 6. Have a total abscess and inflammatory nodule (AN) count of ≥ 3 at the screening and baseline visit.
- 7. Must agree to daily use (throughout the entirety of the study) of one of the following over-the-counter treatments to the body areas affected with HS lesions: either soap and water, or a topical antiseptic wash containing chlorhexidine gluconate, triclosan, or benzoyl peroxide, or a dilute bleach bath.

- 8. Before randomization, a woman must be either:
 - Not of childbearing potential: premenarchal; postmenopausal (>45 years of age with amenorrhea for at least 12 months or any age with amenorrhea for at least 6 months and a serum follicle-stimulating hormone (FSH) level >40 IU/L); permanently sterilized (eg, tubal occlusion, hysterectomy, bilateral salpingectomy); or otherwise be incapable of pregnancy.

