5.2.2. Definition of the Efficacy Endpoints and Calculation of the Efficacy Instruments

5.2.2.1. Hidradenitis Suppurativa Clinical Response (HiSCR)

HiSCR responder status is defined as at least a 50% reduction from baseline in the total abscess and inflammatory nodule count, with no increase in abscess or draining fistula count.

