5.2.3.3.1. Missing Data Binary Endpoints

For binary efficacy endpoints, participants with missing response status will be considered non-responders for all of the efficacy analyses at key visit of Week 16 and over time summaries.

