5.5.2.2. Over Time Summaries

In general, all endpoints with over time analyses will be descriptively summarized by treatment groups using descriptive statistics, such as mean, median, standard deviation, interquartile range, minimum and maximum for continuous variables, and counts and percentages for categorical variables.

Through Week 16

For selected continuous endpoints (change from baseline in AN count, abscess, inflammatory nodule, and draining fistula), Mixed-Effect Model Repeated Measure (MMRM) model will be used and Least Square means (LS means), LS means differences and their corresponding 95% confidence interval will be provided overtime through Week 16 by visit and treatment group in addition to the descriptive summary statistics based on observed data after treatment failures.

From Week 16 through Week 48

For selected continuous endpoints (change from baseline in AN count, abscess, inflammatory nodule, and draining fistula), Mixed-Effect Model Repeated Measure (MMRM) model will be used, Least Square means (LS means) and the corresponding 95% confidence intervals will be provided over time from Week 16 through Week 48 by visit and treatment group in addition to the descriptive summary statistics based on observed data after treatment failures.

Furthermore, for the over time summaries in proportion of participants achieving HiSCR and HS-IGA score of 0 or 1, the corresponding 95% CIs will also be provided for each treatment group at Week 40.

Additionally, the following overtime analyses will be performed at Week 16 DBL with the data available at the time of Week 16 database lock. These analyses will be performed based on the observed data without applying treatment failure rules.

- The proportion of participants who achieved HiSCR from Week 16 through Week 48.
- The change from baseline in total AN count from Week 16 through Week 48.
- The proportion of participants with HS-IGA score of inactive (0), HS-IGA score of inactive (0) or almost inactive (1), and the proportion of participants achieving HS-IGA score of mild activity or better (≤ 2) from Week 16 through Week 48.
- The change from baseline for the past 24 hours pain from Week 16 through Week 48.

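### The protocol says the two doses given to re-randomised placebo participants will be compared, but after Week 16 the SAP reports each dose separately and never the difference

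*SAP*

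**What the plan says.** **Purpose of the two doses.** Placebo participants are re-randomised 1:1 at Week 16, stratified by weight and Hurley stage, to 200 mg SC q4w or to 100 mg SC at Weeks 16, 20, 28 and 36 (Protocol 4.1 and 6.3; SAP 1.5.1). Protocol 4.3 states why: "Comparison of the relative efficacy of these two dose groups will provide useful data" on whether a dose above the psoriasis dose brings added efficacy.

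**Planned comparisons.** SAP 5.1 names each Week 0 guselkumab group against placebo. SAP 5.2.5 defines four groups for Weeks 16 to 48, including the two re-randomised ones, and counts only participants dosed at Week 16 in those two.

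**Reporting after Week 16.** For AN, abscess, inflammatory nodule and draining fistula counts, SAP 5.5.2.2 lists LS means, their differences and intervals through Week 16. For the later period, "Least Square means (LS means) and the corresponding 95% confidence intervals will be provided over time from Week 16 through Week 48" by visit and group, and differences are no longer listed. HiSCR and HS-IGA 0 or 1 get an interval for each group at Week 40.

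**HiSCR in SAP 5.5.4.** The main result "will be summarized by treatment group over time". As an addition, "the HiSCR will be summarized over time from Week 20 through Week 48 with Week 16 as baseline for the placebo participants" re-randomised to either dose. The definition in SAP 5.2.2.1 is unchanged: "HiSCR responder status is defined as at least a 50% reduction from baseline in the total abscess and inflammatory nodule count", with no rise in abscesses or draining fistulas.

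**The concern.** This is the trial's only randomised comparison of two SC doses. The Week 0 arms are 1200 mg IV, 200 mg SC and placebo, so whether more than the psoriasis dose is useful can be answered by randomisation only in the re-randomised groups. The protocol gives that question as a reason for having them, yet the SAP provides no estimate that answers it. A reader is left with two sets of group figures, and the natural shortcut of checking whether the intervals overlap is too strict as a guide to the difference.

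A smaller gap lies in the added Week-16-baseline HiSCR. Inclusion criterion 6 ("Have a total abscess and inflammatory nodule (AN) count of" at least 3) guarantees a usable denominator at Week 0. Nothing guarantees one at Week 16.

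**Working it through.** **1. The plan's only sizing, reproduced.** Inputs: 60 per group, HiSCR 25% and 55%, two-sided 0.05 (Protocol 9.2, Table 1, row 5). The formula is the pooled normal approximation, power = Φ[(d − 1.96·√(2p̄(1−p̄)/n)) / √(p₁(1−p₁)/n + p₂(1−p₂)/n)].
- p̄ = 0.40, so 1.96·√(0.48/60) = 0.175.
- Denominator: √((0.1875 + 0.2475)/60) = 0.0851.
- Power = Φ[(0.30 − 0.175)/0.0851] = 92.9%, against the stated 93%.

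The six rows give 84.1, 94.1, 98.4, 81.6, 92.9 and 98.0%, against 85, 94, 98, 82, 93 and 98%. No stated figure is in doubt. Neither document gives power or precision for 100 mg against 200 mg.

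**2. Precision of the dose difference.** Sixty placebo participants split 1:1 give at most 30 per group. The 50% response rate is my assumption.
- Single group: 1.96·√(0.25/30) = ±17.9 points.
- Difference: 1.96·√(0.50/30) = ±25.3 points. At 40% against 60% it is 1.96·√(0.48/30) = ±24.8.
- With 27 or 24 per group: about ±26 to ±28 points.
- Power at 30 per group for 40% against 60%: 34%. Reaching 80% power needs a difference of about 34 to 36 points.

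**3. Why two group intervals do not replace the difference.** At 50% response, separate intervals stop overlapping only when the gap passes 2 × 17.9 = 35.8 points, but the interval for the difference excludes zero beyond about 25 points. An example with 11/30 and 19/30:
- Group intervals: 19.4 to 53.9% and 46.1 to 80.6%. They overlap.
- Difference: 26.7 ± 24.4 points, that is 2.3 to 51.1. Zero is excluded.

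**4. Week-16-baseline HiSCR when AN is 0 at Week 16.** The reduction is 0/0. If that is treated as missing, SAP 5.2.3.3.1 applies: "participants with missing response status will be considered non-responders". SAP 5.2.2.2 equates a 100% reduction with an AN count of 0, which points towards response. Only participants who stay at AN 0 are affected, because any new abscess or inflammatory nodule is not a 50% reduction under either reading.

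Let f be the share who stay at AN 0, and let the others respond at 50% (assumed). The rate is 0.5(1−f) if they are scored as non-responders and 0.5(1−f) + f if scored as responders, so the gap equals f.
- f = 5%: 47.5% or 52.5%.
- f = 10%: 45% or 55%.

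A chance imbalance can turn the apparent direction. Take 4 of 30 in one group and 1 of 30 in the other staying at 0, with the rest responding at 50%. The rates are 43.3% against 48.3% under non-response, and 56.7% against 51.7% under response.

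The documents do not give f. In an illustrative count model, about 2 to 4% have AN 0 at Week 16 and 14 to 20% have AN below 3. That model assumes a negative binomial baseline with minimum 3 and median 7 to 10, lognormal change, Poisson counts, and 27% of placebo participants with a 50% AN reduction. It gives roughly 1 of 30 with AN 0, and 4 to 6 of 30 below 3.

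**The case against.** **The comparison was never inferential.** The hypotheses, major secondary endpoints and sample size all concern guselkumab against placebo, and Protocol 4.3 promises only useful data. Descriptive reporting is defensible for an unpowered comparison in a proof-of-concept study. This stands as an argument against a test. It is not an argument against an estimate: low precision is better shown by a wide interval than left unstated.

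**A reader can work it out.** The arms are independent and counts will be shown, so an unstratified HiSCR difference can be computed by hand. SAP 5.2.5 says the layout permits assessment between groups. This is correct for HiSCR, so it would be too strong to say that readers can only compare overlap. It does not supply the stratified estimate or the model-based AN-count contrast.

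**SAP 5.1 already promises differences with intervals.** That sentence is general and follows the placebo comparisons. The specific text in 5.5.2.2 lists differences through Week 16 and leaves them out afterwards.

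**On the re-based HiSCR.** A reader might infer that the SAP scores participants with AN 0 at Week 16 as failures. No passage says so. The missing-data rule covers missing status, while a count of 0 at both visits is observed, and the wording for a 100% reduction points the other way. AN 0 is also not the same as lesion-free, since fistulas and non-inflammatory nodules are counted separately. Nor is this summary the main dose analysis: it supplements the Week-0-baseline HiSCR, lesion-count, HS-IGA and patient-reported summaries.

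**Conclusion.** The point holds in a limited form. The protocol gives a dose comparison as a reason for the re-randomisation, and the SAP specifies no between-dose estimate after Week 16. Adding one is a cheap improvement that lets the trial address its own stated question. It corrects no error in the confirmatory analysis and does not touch the primary or major secondary results.

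The estimate will be imprecise: about ±25 points for HiSCR at 30 per group, which is an upper limit on group size, and wider if fewer are dosed at Week 16. These widths assume response near 50% and ignore stratification.

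The AN 0 gap is minor. Scoring is unspecified in one supplementary summary and affects only participants who stay at AN 0, a share the documents do not give. A reader might go further and require AN of at least 3 at Week 16. That is not needed: a 50% reduction is defined for counts of 1 and 2, the entry threshold is not part of HiSCR, and under the illustrative model it would remove 14 to 20% to solve a problem in 2 to 4%.

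**What to change.** **SAP 5.5.2.2.** For the two re-randomised groups, add the 200 mg minus 100 mg difference with 95% CI at Week 40, labelled as estimation without testing, for:
- HiSCR from the Week 0 baseline, using a Mantel-Haenszel difference stratified by weight and Hurley stage, with the Hurley pooling rule of SAP 5.1;
- change in AN count, as a contrast from the Week 16 to 48 MMRM already planned.

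Week 40 is the visit at which the SAP already gives HiSCR intervals. The Week 0 baseline precedes re-randomisation, so it is fair to both doses and avoids the zero-count problem in participants who met criterion 6.

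**SAP 5.5.4.** Limit the Week-16-baseline HiSCR to re-randomised participants with AN above 0 at Week 16 and report the number excluded by group. SAP 5.5.5 uses the same pattern when it limits abscess elimination to those with an abscess at baseline.

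**Cost.** A few lines of SAP text and two table columns, with no new data or model. The drawbacks are a wide interval that must not be read as evidence of equal doses, and a few participants lost from one supplementary summary.

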5.5.5. Analysis Related to Lesion Count

AN Count

- The change from baseline in total AN count, the change from baseline in total AN count by weight, and the change from baseline in total AN count by Hurley stage status will be summarized by treatment groups over time.
- The proportion of participants achieving at least 50%, 75%, 90%, and 100% reduction in total AN count at Week 16 will be compared between each of the guselkumab groups and the placebo group.
- The proportion of participants achieving at least 50%, 75%, 90%, and 100% reduction in total AN count will be summarized by treatment group over time.
- The proportion of participants achieving AN count of 0, 0/1, and 0/1/2 respectively at Week 16 will be compared between each of the guselkumab groups and the placebo group.
- The proportion of participants achieving AN count of 0, 0/1, and 0/1/2, respectively will be summarized by treatment group over time.
- The proportion of participants who experience at least one flare (defined as at least a 25% increase in AN count with a minimum increase of 2 AN relative to baseline) over 16 weeks will be compared between each of the guselkumab groups and the placebo group at Week 16. Furthermore, the proportion of participants who experience at least one flare over 48 weeks will be summarized at Week 48 by treatment groups.

In addition, the change from baseline in AN count by prespecified anatomic region and treatment group will be summarized at Week 16 and Week 40.

Abscess

- The proportion of participants who achieved complete elimination of abscesses at Week 16 will be compared between each of the guselkumab groups and the placebo group among participants who had any abscess at baseline.
- The change from baseline in number of abscesses at Week 16 will be compared between each of the guselkumab groups and the placebo group.

- The change from baseline in number of abscesses will be summarized by treatment group over time.

Fistulas

- The proportion of participants who achieved complete elimination of draining fistulas at Week 16 will be compared between each of the guselkumab groups and the placebo group among those with draining fistulas at baseline.
- The change from baseline in number of draining fistulas at Week 16 will be compared between each of the guselkumab groups and the placebo group.
- The change from baseline in number of draining fistulas will be summarized by treatment group over time.

Inflammatory and non-inflammatory Nodules

- The proportion of participants who achieved complete elimination of inflammatory nodules at Week 16 will be compared between each of the guselkumab groups and the placebo group among those with inflammatory nodules at baseline.
- The change from baseline in number of inflammatory nodules at Week 16 will be compared between each of the guselkumab groups and the placebo group.
- The change from baseline in number of inflammatory nodules will be summarized by treatment group over time.
- The change from baseline in number of non-inflammatory nodules at Week 16 will be compared between each of the guselkumab groups and the placebo group among pts with non-inflammatory nodules at baseline.
- The change from baseline in number of non-inflammatory nodules will be summarized by treatment group over time.

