5.2.3. Data Handling Rules

The following treatment failure rules and data handling rules will be applied to the efficacy analyses in this study.

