5.2.3.1. Treatment Failure Criteria

Participants who discontinue study intervention due to lack of efficacy or an AE of worsening of HS, or who started a protocol-prohibited medication or therapy during the study that could improve HS, are considered treatment failures.

The particular protocol-prohibited medications/therapies include:

Systemic Therapies:

- Any immunodulatory biologic therapy
- Any conventional systemic immunosuppressive therapy
- Any systemic corticosteroid for HS
- Any systemic antibiotic therapy for HS or any indications other than infection
- Any systemic retinoid

- Investigational Agents for HS
- Analgesic therapy for HS (Section 5.2.3.2.1)
- Phototherapy (PUVA and/or UVB) for any indications and other phototherapies for indication of HS

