5.2.3.2. Treatment Failure Rules

A participant who meets one or more of the treatment failure criteria specified in Section 5.2.3.1 will be considered a treatment failure from that point onward. The baseline values will be used for all directly measured endpoints regardless of the actual measurements. Zero will be assigned to improvement, and non-responder status will be assigned to binary response variables. However, treatment failure rules for the HSSD pain related endpoints will be handle differently and are specified in Section 5.2.3.2.1.

Treatment failure is assumed to have occurred at the earlier of the following dates:

- Date of discontinuation of study treatment due to lack of efficacy or an AE of worsening of HS or
- Date of initiation of a protocol-prohibited medication/therapy during the study that could improve HS.

In addition, lesions that received intervention as rescue therapy will be counted as present after the visit of intervention.

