5.2.4.1. Composite Strategy

The Composite Strategy assesses the treatment effects not only based on the variable measurements, but also based on intercurrent event defined in TF criteria. If a participant meets TF criteria, participant will be a non-responder for binary response variables and no improvement will be assigned for continuous variables.

- **Composite Estimand (Continuous)**

Variables: The endpoint is defined as change for baseline score. No improvement (zero change) will be assigned after a subject meets one or more treatment failure criteria.

Intercurrent Events: the intercurrent events are captured through variable definition.

Population level summary: difference in mean changes from baseline between a guselkumab group and placebo group.

- **Composite Estimand (Binary)**

Variables: The endpoint (e.g. HiSCR) is defined as the proportion of participants achieving a response. No responder status will be assigned after a subject meets one or more TF criteria.

Intercurrent Events: the intercurrent events are captured through variable definition.

Population level summary: difference in proportion of responders between a guselkumab group and placebo group.

The composite strategy will be used for analyzing all efficacy endpoints.

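### Setting AN count to baseline after treatment failure classes a first flare seen after failure as no flare

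*SAP*

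**What the plan says.** SAP 5.5.5 defines flare as an unfavourable event built from the AN count: "at least one flare (defined as at least a 25% increase in AN count with a minimum increase of 2 AN relative to baseline". The proportion with a flare over 16 weeks is compared between each guselkumab group and placebo, and the proportion over 48 weeks is summarised. The section has no rule for flare status after treatment failure or with missing counts.

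The general rules therefore govern. SAP 5.2.3 opens: "The following treatment failure rules and data handling rules will be applied to the efficacy analyses in this study". Under 5.2.3.1, treatment failures include "Participants who discontinue study intervention due to lack of efficacy or an AE of worsening of HS", as well as those who start a listed prohibited therapy. Under 5.2.3.2 such a participant "will be considered a treatment failure from that point onward". For measured quantities, "The baseline values will be used for all directly measured endpoints regardless of the actual measurements". For the rest, "Zero will be assigned to improvement, and non-responder status will be assigned to binary response variables". SAP 5.2.4.1 restates this as an estimand ("If a participant meets TF criteria, participant will be a non-responder for binary response variables and no improvement will be assigned for continuous variables") and gives it full scope: "The composite strategy will be used for analyzing all efficacy endpoints".

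For missing status on binary endpoints, SAP 5.2.3.3.1 and 5.5.3 again assign non-responder. SAP 5.5.2.1 refers to Section 5.1 for the definition of non-responder imputation, but 5.1 contains none. The places where the SAP limits or sets aside the failure rules do not name flare: 5.2.3.2.1 for HSSD pain, 5.5.2.2 for some Week 16 database-lock summaries, 5.5.4 for HiSCR, and 5.5.8 for hs-CRP and Hurley stage.

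**The concern.** The failure rules are written for favourable outcomes. For a responder endpoint or an improvement score, returning to baseline denies the participant credit. For flare, where the event is a rise above baseline, the same step removes the event. Two of the triggers, lack of efficacy and an AE of worsening HS, describe participants in whom a later AN rise is plausible.

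At stake is whether the Week 16 flare comparison and the Week 48 flare summary show the flares that were actually counted. A participant who stops for worsening and then has a first qualifying rise would appear in the table as not having flared.

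**Working it through.** The documents state no flare rate, so there is no figure to reproduce. The check applies the definition before and after the reset.

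**Inputs.** Flare: rise of at least 25% and at least 2 (SAP 5.5.5). Minimum baseline AN: 3 (Protocol 5.1, criterion 6). Planned arm size: 60 (SAP 1.4). Placebo re-randomised 1:1 at Week 16 (SAP 1.5.1). Lesions counted at each visit (Protocol 8.1.2). Follow-up about 12 weeks after the last dose (Protocol 7.1).

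**Step 1: can a flare occur after the reset?** For baseline B, the smallest qualifying rise is max(2, 0.25 × B rounded up). After the reset the rise is B − B = 0.

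| Baseline AN | 25% of baseline | Smallest qualifying rise | Smallest flare count | Rise after reset |
|---|---|---|---|---|
| 3 | 0.75 | 2 | 5 | 0 |
| 8 | 2.0 | 2 | 10 | 0 |
| 10 | 2.5 | 3 | 13 | 0 |
| 20 | 5.0 | 5 | 25 | 0 |

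Zero is below 2 at every baseline, so no flare can be recorded after failure.

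**Step 2: a hypothetical participant.** Baseline AN is 8. At Week 8 AN is 9 (+1, 12.5%, not a flare) and treatment stops for an AE of worsening HS. At Week 12 AN is 12 (12 − 8 = +4; 4/8 = 50%). If the last dose was at Week 4, follow-up runs to about Week 4 + 12 = Week 16, so the Week 12 count is collected.

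| Rule applied | Status |
|---|---|
| Observed counts | Flare |
| AN reset to baseline | No flare |
| Non-responder read as event not met | No flare |
| Non-responder read as unfavourable outcome | Flare |

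The plan's wording thus leads to two possible outcomes, and two of its three routes give no flare.

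**Step 3: step size.** One participant classified differently moves a Week 16 arm by 1/60 = 1.7 points. In the Week 48 summary a placebo crossover group has at most about 60/2 = 30, so one participant moves it by about 1/30 = 3.3 points, or more if the group is smaller.

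**Step 4: direction (all counts assumed).** Suppose 18 placebo and 12 guselkumab participants flare before, or without, treatment failure. Under the reset the difference is 18/60 − 12/60 = 30.0 − 20.0 = 10.0 points. Now add participants whose first rise is observed after failure:

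| First rises after failure, placebo / guselkumab | Observed rates | Difference |
|---|---|---|
| 6 / 2 | 24/60 − 14/60 = 40.0% − 23.3% | 16.7 |
| 4 / 4 | 22/60 − 16/60 = 36.7% − 26.7% | 10.0 |
| 2 / 6 | 20/60 − 18/60 = 33.3% − 30.0% | 3.3 |

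The reset can shrink the difference, leave it unchanged or enlarge it. Only the balance of such participants between arms decides, and the documents do not give it.

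**The case against.** The strongest reply is that the reset is the SAP's own strategy carried through. The continuous estimand in 5.2.4.1 assigns zero change after failure, so the plan never records worsening after failure for any count or score, and flare merely inherits that. This stands. A reader might infer that the plan contradicts its composite strategy, but for AN count it follows it. The point is what that strategy does to an event defined as a rise.

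A reader might also infer a three-way ambiguity. The documents do not support that. The reset and the event-not-met reading of non-responder give the same status. The reading that gives flare fits poorly, because the SAP ties non-responder to response variables and flare is not a response.

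Flares before failure are kept. Because lesions are counted at each visit before dosing (Protocol 1.3, footnote c), some participants who stop for worsening will already have a qualifying count. SAP 5.2.3.2 does not say whether a count on the failure date itself is kept. The number affected may therefore be small, possibly zero.

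Flare is also absent from the protocol's endpoint list. It is an additional SAP analysis, which Protocol 9.4.2.3 permits. After Week 16, placebo participants are included only if they crossed over and received guselkumab (SAP 5.2.5, 5.5.2), so those who stopped earlier are not in the later groups. All of this limits the reach; none of it restores a counted flare that the rule removes.

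**Conclusion.** The concern holds as a minor one. Followed as written, the plan classes a first qualifying AN rise counted after treatment failure as no flare, although the rise was observed. That conclusion follows from the text and needs no assumed rates.

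The effect is 1.7 points per participant in a Week 16 arm, assuming the planned 60 per arm. A reader might infer that the flare result is biased towards guselkumab or that harm is concealed. The documents support neither: the direction depends on unknown counts by arm, and worsening remains visible in the reasons for discontinuation (SAP 4.2) and the AE listings (SAP 6.1). Only the Week 16 flare comparison, with its nominal p-value (SAP 5.5), and the descriptive Week 48 summary are touched.

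**What to change.** Add to SAP 5.5.5, for flare only:

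1. **Main analysis.** Do not use the baseline-value reset. Derive flare from all observed AN counts in the window regardless of treatment failure, and keep the existing rule that lesions given rescue intervention count as present.
2. **Sensitivity analysis for failures.** Count participants who discontinue for lack of efficacy or an AE of worsening HS as flare. Counting every treatment failure as flare may be offered as an option but should not be the main analysis. SAP 5.2.3.1 includes, for example, phototherapy for any indication, and a participant with a falling AN count would then be reported as flaring.
3. **Incomplete counts.** In place of the non-responder rule in 5.2.3.3.1 and 5.5.3, classify participants with incomplete counts and no observed flare on the counts available, show their number by arm, and count them as flare in a sensitivity analysis. Those sections stay unchanged for HiSCR and the other response endpoints.

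The cost is a short paragraph, one derived flag and one or two extra tables. No new data are needed, and the SAP already summarises HiSCR without the failure rules (5.5.4). There are two downsides. Counts after a prohibited therapy may be lowered by it. Early stoppers will also have incomplete counts: follow-up after a last dose at Week 0 reaches only about Week 12, after Week 4 about Week 16, and the gap is wider towards Week 48.
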